5.3.2. Continuous Endpoints

For non-PRO continuous endpoints measured longitudinally, missing values post-baseline will not be imputed explicitly. For longitudinal continuous endpoints, assuming that the missing data mechanism is missing at random (MAR), the data will be analyzed based on a restricted maximum likelihood (REML) using a linear mixed-effect model with repeated measures for these continuous variables (see [Section 5.2.3](#)). This model will yield valid inferences in the presence of a missing data mechanism that is MAR.

For the continuous PRO variables such as pruritus NRS, DLQI/CDLQI, POEM, PSAAD, HADS, EQ-5D-5L/EQ-5D-Y, SF-36v2 and FACIT-F, rules suggested by the developers of these instruments will be followed in calculating the missing values. If these rules are not enough for imputing a value, then the missing values will be handled in the same way as non-PRO variables.

5.3.3. Time to Event Endpoints

For time-to-event endpoints, subjects who complete the study without the event of interest or those who withdraw before experiencing the event of interest will have their event times right censored at the last available measurement time (or visit) used to define whether the subject experienced the associated event (ie, the event of interest is presumed to have occurred beyond this time point).

6. ANALYSES AND SUMMARIES

Analysis will be done pairwise between each of the PF-04965842 QD treated groups (200 mg and 100 mg) and placebo (two separate tests of hypotheses). An analysis with point estimates of the difference and the associated 95% confidence intervals will also be done for PF-04965842 200 mg QD versus PF-04965842 100 mg QD without testing any hypotheses.

A summary of analyses for clinical efficacy endpoints is provided in [Appendix 1](#). Visit windows to be used for all efficacy analyses and some relevant safety analyses are detailed in [Appendix 2](#).

Data collected at Week 16 will be displayed in listings only, and will not be part of any analyses, unless specifically noted otherwise.

6.1. Co-primary Endpoint - Week 12 IGA Response

6.1.1. Primary Analysis

- Summary: Proportion of subjects achieving IGA response at Week 12
- Population: FAS
- Statistical Method: CMH and normal approximation in [Section 5.2.1](#)
- Missing Data: Missing data arising due to subject dropout are considered “non-response” and intermittent missing data will remain missing.(see [Section 5.3.1](#))

6.1.2. Additional/Supportive Analysis

- Additional analyses of the Week 12 IGA response are:
- The proportion of subjects achieving IGA response at Week 12 will be analyzed using the CMH and normal approximation method in [Section 5.2.1](#) for the PPAS population.

- Results of proportion of subjects achieving the IGA response at Week 12 will be obtained from the FAS population using a tipping point analysis where all missing responses will be multiply imputed (which will consider analyses under MAR as well as MNAR as described in Section 5.3.1 and Appendix 3).

6.2. Co-primary Endpoint - Week 12 EASI-75 Response

6.2.1. Primary Analysis

- Summary: Proportion of subjects achieving EASI-75 response at Week 12.
- Population: FAS.
- Statistical Method: CMH in Section 5.2.1
- Missing Data: Missing data arising due to subject dropout are considered “non-response” and intermittent missing data will remain missing. (see Section 5.3.1)

6.2.2. Additional/Supportive Analyses

- Additional analyses of the Week 12 EASI-75 response are:
- The proportion of subjects achieving EASI-75 response at Week 12 will be analyzed using the CMH and normal approximation method in Section 5.2.1 for the PPAS population
- Results of proportion of subjects achieving the EASI-75 at Week 12 will be obtained from the FAS population using a tipping point analysis where all missing responses will be multiply imputed (which will consider analyses under MAR as well as MNAR as described in Section 5.3.1 and Appendix 3)

6.3. Key Secondary Efficacy Endpoints

6.3.1. Weeks 2, 4 and 12 NRS4 for severity Response

- Summary: Proportion of subjects with NRS4 for severity response at Week 2, 4 and 12.
- Population: Subjects from the FAS, PPAS with a baseline NRS score for severity ≥ 4 .
- Statistical Method: CMH and normal approximation in Section 5.2.1. Visit windows will be used as described in Appendix 2.
- Missing Data: Two analyses will be performed:
- Primary Analysis: Missing data arising due to subject dropout are considered “non-response”. For any other missing observations, a multiple imputation approach based on a GLMM will be used. (see the last two paragraphs within Section 5.3.1). This analysis will be based on both the FAS and the PPAS.

- Sensitivity Analysis: All missing data will be considered as “non-response”. This analysis will be based on the FAS only.

6.3.2. Week 12 Change from Baseline in PSAAD

- Summary: Change from baseline at Week 12.
- Population: FAS, PPAS.
- Statistical Method: MMRM in [Section 5.2.3](#). As PSAAD is collected daily, data will be summarized weekly using a simple average of the values recorded within a week. In the implementation of the MMRM models, data from all weekly visits will be used
- Missing Data: Observed Data

6.4. Secondary Efficacy Endpoints

6.4.1. Week 8 NRS4 for severity Response

- Summary: Proportion of subjects with NRS4 for severity response at Week 8
- Population: Subjects from the FAS with a baseline NRS score for severity ≥ 4
- Statistical Method: CMH and normal approximation in [Section 5.2.1](#). Visit windows will be used as described in [Appendix 2](#)
- Missing Data: Two analyses will be performed:
- Primary Analysis: Missing data arising due to subject dropout are considered “non-response”. For any other missing observations, a multiple imputation approach based on a GLMM will be used. (see the last two paragraphs within [Section 5.3.1](#)). This analysis will be based on both the FAS and the PPAS.
- Sensitivity Analysis: All missing data will be considered as “non-response”. This analysis will be based on the FAS only.

6.4.2. Time to Achieve NRS4 for severity

- Summary: Time to achieve a ≥ 4 -point improvement in the pruritus NRS for severity from baseline:
- Population: Subjects from the FAS with a baseline NRS score for severity ≥ 4 .
- Statistical Method: Analyses for Time to Event Data in [Section 5.2.5](#).
- Missing Data: See [Section 5.3.3](#).

6.4.3. Weeks 2, 4, 8 and 12 IGA Responses

- Summaries:

- Proportion of subjects with Weeks 2, 4, 8 and 12 IGA response based on the IGA for clear (0).
- Proportion of subjects with Weeks 2, 4 and 8 IGA response based on the IGA for clear (0) or almost clear (1) and a reduction from baseline of ≥ 2 points.
- Population: FAS.
- Statistical Method: CMH and normal approximation in [Section 5.2.1](#)
- Missing Data: Missing data arising due to subject dropout are considered “non-response” (see [Section 5.3.1](#))

6.4.4. Weeks 2, 4, 8 and 12 EASI-50 / EASI-90 / EASI-100 Response

- Summary: Proportion of subjects with Weeks 2, 4, 8 and 12 EASI-50 / EASI-90 / EASI-100 response.
- Population: FAS.
- Statistical Method: CMH and normal approximation in [Section 5.2.1](#).
- Missing Data: Missing data arising due to subject dropout are considered “non-response” (see [Section 5.3.1](#)).

6.4.5. Weeks 2, 4 and 8 EASI-75 Response

- Summary: Proportion of subjects with Weeks 2, 4 and 8 EASI-75 response.
- Population: FAS.
- Statistical Method: CMH and normal approximation in [Section 5.2.1](#).
- Missing Data: Missing data arising due to subject dropout are considered “non-response” (see [Section 5.3.1](#)).

6.4.6. Weeks 2, 4, 8 and 12 Change from Baseline in Total EASI Score, Pruritus NRS, %BSA, Total SCORAD Score, SCORAD (VAS) of Sleep Loss

- Summary: Change (or percent change) from baseline in Total EASI Score, Pruritus NRS, %BSA, Total SCORAD Score, SCORAD (VAS) of Sleep Loss at Weeks 2, 4, 8 and 12.
- Population: FAS.
- Statistical Method: MMRM in [Section 5.2.3](#)
- Missing Data: Observed Data.

6.4.7. Weeks 2, 4, 8 and 12 Proportion with %BSA <5%

- Summary: Proportion of subjects with %BSA <5% at Weeks 2, 4, 8 and 12.
- Population: FAS.
- Statistical Method: CMH and normal approximation in [Section 5.2.1](#).
- Missing Data: Missing data arising due to subject dropout are considered “non-response” (see [Section 5.3.1](#)).

6.4.8. Weeks 2, 4, 8 and 12 SCORAD50 / SCORAD75 Response

- Summary: Proportion of subjects with Weeks 2, 4, 8 and 12 SCORAD50 / SCORAD75 response.
- Population: FAS.
- Statistical Method: CMH and normal approximation in [Section 5.2.1](#).
- Missing Data: Missing data arising due to subject dropout are considered “non-response” (see [Section 5.3.1](#)).

CCI [REDACTED]

[REDACTED]

| [REDACTED]

[REDACTED]

| [REDACTED]

| [REDACTED]

| [REDACTED]

[REDACTED]

| [REDACTED]

| [REDACTED]

| [REDACTED]

| [REDACTED]

CCI [Redacted]

- | [Redacted]
- | [Redacted]
- | [Redacted]
- | [Redacted]
- | [Redacted]
- | [Redacted]
- | [Redacted]
- | [Redacted]
- | [Redacted]

[Redacted]

- | [Redacted]
- | [Redacted]
- | [Redacted]
- | [Redacted]

CCI [Redacted]

- | [Redacted]
- | [Redacted]
- | [Redacted]
- | [Redacted]

[Redacted]

- | [Redacted]

[REDACTED]

[REDACTED]

[REDACTED]

[REDACTED]

[REDACTED]

[REDACTED]

[REDACTED]

[REDACTED]

[REDACTED]

[REDACTED]

[REDACTED]

[REDACTED]

[REDACTED]

[REDACTED]

[REDACTED]

[REDACTED]

[REDACTED]

[REDACTED]

[REDACTED]

6.7. PK Endpoints

Population PK data for PF-04965842 will be summarized through appropriate data tabulations, descriptive statistics, and graphical presentation. A population PK model will be developed for the purpose of estimating PK parameters. Additional details of the methodology will be captured in a separate modeling plan and the results will also be reported separately.

6.8. Subset Analyses

Summary statistics for co-primary endpoints will be presented by subgroups below.

- Age (years) group (<18, ≥18; <40, ≥40; <65, ≥65);
- Sex (Male, Female);

- Race (White, Black or African-American, Asian, Other²);
- Weight (kg) (less than or equal to the median value in FAS, above the median value);
- Region of enrollment (US/Canada/Australia, EU, Asia);
- AD Duration (years) group (<26, ≥26);
- Baseline disease severity (moderate, severe);
- Baseline EASI group (16-25, >25);
- Baseline % BSA group (10-30, >30-50, >50);
- Previous use of systemic immunosuppressant for AD (Yes, No).

Estimates of the difference between the active dose groups and placebo, along with the 95% confidence interval (no p-value), will be presented for each defined category of each subgroup. Analyses will be performed using the normal approximation to the binomial distribution, without any adjustments for randomization strata.

The primary purpose of the subgroup analyses is to check for consistency of results across subgroups, to make sure overall results are not being driven by some subset of subjects.

Graphical display (eg, forest plots) of the differences between treatment groups will be presented. There is no intention to have any specific inference within subgroups.

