9.1. Sample Size Determination

Sample size for the study was based on the co-primary endpoints. A total sample of 375 subjects with 150 subjects randomized to PF-04965842 200 mg QD, 150 subjects randomized to PF-04965842 100 mg QD and 75 subjects randomized to placebo (2:2:1 randomization) would provide at least 95% power to detect a difference in IGA response rate of at least 20% between PF-04965842 200 mg QD (or PF-04965842 100 mg QD) and placebo, assuming the placebo response rate is 6% at Week 12. Furthermore, this will also provide at least 99% power to detect a difference in EASI-75 response rate of at least 30% between PF-04965842 200 mg QD (or PF-04965842 100 mg QD) and placebo, assuming the placebo response rate is 15% at Week 12.

The Type-I error for testing each individual co-primary endpoint was fixed at 5%. Since both endpoints are co-primary, the study will meet its primary endpoint only if both hypotheses (corresponding to each co-primary endpoint) are rejected. Therefore, the Type-I error rate remains controlled at 5% for testing the primary endpoint. The power to reject both hypotheses when a true difference exists (alternative hypothesis is true) could be at least 94% depending on the correlation between the endpoints.

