5.2.1. Analyses of Binary Data

Binary data at each scheduled visit will be analyzed by two approaches: (1) the test of hypothesis (and the p-value) between the PF-04965842 treatment groups versus the placebo group will be conducted by the Cochran-Mantel-Haenszel (CMH) statistic adjusting for the effect of randomization strata; p-values from the CMH statistic will be used to establish the superiority of each dose of PF-04965842 to placebo in binary responses; and (2) the proportion of responders in the PF-04965842 treatment groups versus the placebo group will be summarized by the difference and its 95% confidence interval obtained by normal approximation. The difference in proportions will be calculated within each randomization stratum. The final estimate of the difference in proportions will be a weighted average of these stratum-specific estimates using CMH weights. The CMH weight w_k for stratum k ($k = 1, 2, 3, 4$) is given by,

$$w_k = \frac{\frac{n_{ik} n_{ck}}{n_{ik} + n_{ck}}}{\sum_{j=1}^4 \frac{n_{ij} n_{cj}}{n_{ij} + n_{cj}}}$$

where n refers to sample size, the subscript c refers to a comparator group (eg, placebo) and the subscript i refers to a test group (eg, either the low or high doses (so that two test statistics are calculated, one for each dose versus placebo). The difference is estimated as $\hat{d} = \sum_{k=1}^4 w_k (\hat{p}_{ik} - \hat{p}_{ck})$, where \hat{p} refers to the estimated relative frequency. An estimate for \hat{p} is obtained as x/n , where x is the number of responders.

Two-sided 95% confidence intervals for the difference (based on a normal approximation) are formed by:

$$\hat{d} \pm 1.96 \sqrt{\sum_{k=1}^4 w_k^2 \left(\frac{\hat{p}_{ik}(1 - \hat{p}_{ik})}{n_{ik}} + \frac{\hat{p}_{ck}(1 - \hat{p}_{ck})}{n_{ck}} \right)}$$

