In the above formula for the variance of \hat{d} (under the square-root sign), when the number of responders is zero ($x = 0$), then \hat{p} will be replaced by $0.5/(n + 1)$. This change will be made only for calculating the variance of \hat{d} and not anywhere else. Estimates of the difference in proportions along with the two-sided 95% confidence interval will also be provided for the PF-04965842 200 mg QD group versus the PF-04965842 100 mg QD group. No hypotheses will be tested. In analyses of responders, 95% confidence intervals will be calculated for the estimated proportion of response. The confidence interval is based on the normal approximation (or the Clopper-Pearson exact method when there are no or 100% responders).

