5.2.6. Analyses of Tier-1 and Tier-2 Events

Number and percentage of subjects with AEs over the duration of treatment will be provided for each treatment group. Tier-1 events will be analyzed using exact methods proposed by Chan and Zhang (1999). Tier-2 events will be analyzed using asymptotic methods proposed by Miettinen and Nurminen (1985). Risk differences (each PF-04965842 dose compared to placebo) and 2-sided 95% confidence intervals will be reported. P-values will also be reported for Tier-1 events. Tier-3 events will not be summarized separately but included within the summary of all AEs.

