7. INTERIM ANALYSES

There will be no interim analyses for this study.

This study uses an External Data Monitoring Committee (E-DMC). The E-DMC will be responsible for ongoing monitoring of the efficacy, safety and PKs of subjects in the study according to the charter. Pharmacokinetic data from the first 20 adolescent subjects will be analyzed and reviewed by the E-DMC. The recommendations made by the E-DMC to alter the conduct of the study will be forwarded to Pfizer for final decision. Pfizer will forward such decisions, which may include summaries of aggregate analyses of endpoint events and of safety data that are not endpoints, to regulatory authorities, as appropriate. Composition of the E-DMC and processes under which the E-DMC operates will be documented in the E-DMC charter.

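### Do the subgroup intervals in SAP 6.8 need their own zero-responder rule or a different interval method?

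*SAP*

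**What the plan says.** SAP 6.8 lists ten grouping variables with 28 categories in all (age is split three ways). Each category gets the difference between each dose and placebo with a 95% interval, no p-value, and a forest plot. The method sentence is "Analyses will be performed using the normal approximation to the binomial distribution, without any adjustments for randomization strata". The section sets no minimum category size and does not refer back to 5.2.1. It describes the purpose as a check on consistency, and adds: "There is no intention to have any specific inference within subgroups".

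The only interval for a difference in response proportions that the SAP writes out is in 5.2.1, introduced by "Two-sided 95% confidence intervals for the difference (based on a normal approximation) are formed by". It is the CMH-weighted sum over four strata. Directly below it, "when the number of responders is zero", the estimated proportion is replaced by 0.5/(n+1). The scope is then limited: "This change will be made only for calculating the variance of" the estimated difference, and nowhere else. The Clopper-Pearson fallback in the same section concerns a single proportion, not a difference.

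**The concern.** The Wald interval for a difference behaves badly when a cell is empty, because an arm with no responders contributes no variance. If both arms are empty, the interval collapses to a point. The sponsor provides for this in 5.2.1, yet 6.8, where small cells are most likely, is silent. The legible binary analyses in SAP 6.1 to 6.4 point to 5.2.1; 6.8 does not. A programmer could also take the scope limit on the rule to exclude other tables.

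Small rows are plausible. The planned placebo arm is only 75, and categories such as under 18, 65 and over, and some race groups may be thin. The one adolescent count in the SAP is in Section 7: "Pharmacokinetic data from the first 20 adolescent subjects will be analyzed and reviewed by the E-DMC". At 2:2:1, 20 subjects would be 8, 8 and 4.

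At stake is how the forest plot reads. A row that is too narrow, or has no width, would look precise when it is among the least informative, and with no p-value the interval is the only display of its uncertainty.

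**Working it through.** **Inputs.** Protocol 9.1 and SAP 2.2: 150, 150 and 75 subjects, so two active per placebo in each comparison; IGA 26% versus 6%; EASI-75 45% versus 15%. SAP 5.2.1: multiplier 1.96 and the 0.5/(n+1) rule. Assumed: placebo subjects per category (3 to 37, active twice that), and the half-effect and no-effect rates.

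**The plan's own figures.** Power = Φ[(δ − 1.96·SE0)/SE1], with SE0 pooled and SE1 unpooled.
- IGA: pooled rate (39 + 4.5)/225 = 0.1933; SE0 = 0.0558; SE1 = 0.0451; (0.20 − 0.1095)/0.0451 = 2.01; power 97.8% (stated: at least 95%).
- EASI-75: pooled rate 0.35; SE0 = 0.0675; SE1 = 0.0579; (0.30 − 0.1322)/0.0579 = 2.90; power 99.8% (stated: at least 99%).

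Both statements hold.

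**What 5.2.1 becomes with one stratum.** The single CMH weight is 1, so the interval is d ± 1.96·√[pa(1−pa)/na + pc(1−pc)/nc], where d = pa − pc. This is exactly the unstratified normal-approximation interval. The two readings differ only in whether a zero proportion becomes 0.5/(n+1) under the root.

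**Two examples.**
- 5/20 active, 0/10 placebo. Plain: SE = √(0.25×0.75/20) = 0.097, giving 0.06 to 0.44. With the rule, the placebo proportion is 0.5/11 = 0.045 and SE = 0.117, giving 0.02 to 0.48.
- 0/8 active, 0/4 placebo. Plain: a point at 0. With the rule, the proportions are 0.5/9 and 0.5/5 and SE = 0.170, giving −0.33 to 0.33.

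**Exact coverage at the planning rates**, summing both binomials over all outcomes:

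| Active vs placebo | IGA plain | IGA with rule | EASI-75 plain | EASI-75 with rule |
|---|---|---|---|---|
| 6 vs 3 | 82.2% | 99.0% | 91.9% | 93.6% |
| 8 vs 4 | 87.9% | 98.9% | 93.1% | 93.5% |
| 10 vs 5 | 92.7% | 96.3% | 91.1% | 92.1% |
| 12 vs 6 | 92.2% | 97.3% | 87.6% | 93.5% |
| 16 vs 8 | 92.2% | 95.0% | 89.7% | 93.5% |
| 3–8 placebo, range | 82.2–94.9% | 95.0–99.0% | 87.6–93.1% | 92.1–93.7% |
| 15–37 placebo, range | 92.6–95.3% | 94.6–96.1% | 92.8–94.3% | 93.2–94.4% |

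Zero-width IGA interval, plain: 0.74⁸ × 0.94⁴ = 7.0% at 8 vs 4 and 0.74¹⁶ × 0.94⁸ = 0.5% at 16 vs 8. With the rule it is effectively nil.

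**Other true rates, 3–8 placebo subjects:**

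| True rates | Plain | With rule |
|---|---|---|
| IGA 16% vs 6% | 69.8–93.6% | 98.3–99.2% |
| IGA 6% vs 6% | 97.6–99.2% | 99.3–99.9% |
| EASI-75 30% vs 15% | 85.6–92.7% | 94.2–96.7% |
| EASI-75 15% vs 15% | 89.0–94.6% | 96.2–98.1% |

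At IGA 6% vs 6%, 22.7–57.3% of plain intervals are a single point at 0, which happens to count as covering.

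**Would another method gain anything?** At 3–8 placebo subjects and the planning rates, Miettinen-Nurminen covers 96.6–98.6% for IGA and 96.5–97.4% for EASI-75, which is 1.5 to 3.6 points above nominal. The rule-based interval is 1.3 to 2.9 points below nominal on EASI-75 and at or above nominal on IGA. Mean IGA width at 16 vs 8 is 0.57 with the rule and 0.64 with Miettinen-Nurminen.

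**The case for a change.** The strongest case for a change is that the text leaves two readings open and the choice between them alters the printed interval. The poor plain-Wald figures are right, a subgroup row is where an empty cell is likeliest, and one sentence, or the Miettinen-Nurminen method that SAP 5.2.6 already names, would settle it.

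The missing cross-reference and the arithmetic stand. The inference from them does not. Section 5 of the SAP is its general methodology, and 5.2.1 is its method for binary data. The phrase in 6.8 about not adjusting for strata removes a feature that, among the intervals the SAP writes out, only the 5.2.1 interval has, so it reads as 5.2.1 with one stratum. The scope limit in 5.2.1 keeps 0.5/(n+1) out of the point estimate; it governs where in the calculation the substitution goes, not which tables use it. An analyst who met a zero-width row would in any case look to 5.2.1 first.

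The worst figures therefore need the less natural reading and very small categories together. Three to eight placebo subjects is 4% to 11% of the planned 75. Splits such as sex, median weight or baseline severity give no reason to expect that. The 20 adolescents in Section 7 trigger a pharmacokinetic review and are not a planned subgroup size.

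Nor is plain-Wald under-coverage purely a small-category effect. At IGA 6% vs 6% it covers 97.6–99.2% with 3–8 placebo subjects but 91.3–95.4% with 15–37.

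**Conclusion.** No change follows. SAP 6.8 omits a cross-reference, and the sensible way to fill it is already in the SAP. On that reading no zero-width rows are to be expected. At the planning rates with 3 to 8 placebo subjects, IGA coverage is at or above nominal and EASI-75 falls short by 1.3 to 2.9 points. A shortfall of that size in a few descriptive rows, with no p-values and no intended inference, changes no decision, error rate or primary result.

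Switching to Miettinen-Nurminen is a matter of preference. It exchanges slight under-coverage on EASI-75 for slight over-coverage, widens the IGA rows, and makes the subgroup rows differ in method from the overall 5.2.1 result they are compared with.

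The conclusion rests on reading 6.8 as the one-stratum case of 5.2.1. The sizes quoted rest on assumed category counts at a 2:1 ratio and on the planning rates. If the rule were left out, the harm would still be confined to how a few very small forest-plot rows look.
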